13.2.3. Other Variables

Discontinuations

The difference between treatments, both overall and for each primary reason, will be compared by using a 2-sided Fisher's exact test.

Demographic and Baseline Characteristics

Comparisons between treatment groups of continuous variables will be made by using a one-way analysis of variance with treatment as a factor. For categorical variables, the Fisher's exact test will be used. All tests will be 2-sided and performed at the 0.05 level of significance.

Time-to-Event Data

Time-to-event endpoints including time-to-complete-wound-closure/healed will be evaluated using the Kaplan-Meier method. The log-rank test will be used to compare the distributions between two treatment groups, stratified by the ulcer size (1 cm² to ≤ 3 cm² vs. > 3 cm² to 12 cm²).

Rate of Wound Closure, as Assessed by Computerized planimetry

Analysis of Covariance (ANCOVA) will be used to compare the rate of wound closure (as defined in section 13.2.2 for the two treatment groups. The stratification factor, ulcer size at the time of randomization, will be used in this analysis. Other covariate, as outlined in section 11.4, may also be incorporated in the model, if their presence is statistically significant (i.e. p-value ≤ 0.05).

Safety Data

The primary safety endpoint for this study is any severe device-related complication where relationship to the device was assessed by the clinical event committee possible, probably, or definite. Fisher's exact test will be used to compare incidence rates of serious device-related complications as well as for any device-related complication, and for specific complications between the treatment group and the control group.

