	
 
1. 46% of DFUs managed with the Active Treatment achieve complete wound closure by 12 weeks.
 
2. 26% of DFUs managed with SOC achieve complete wound closure by 12 weeks.
 
 
To accommodate the potential early discontinuations, the trial proposes to randomize 256 subjects (128 per treatment).
 
Overall 2-sided Type I Error rate (alpha) of 0.05.
 
A single interim analysis, when 50% of subjects complete the trial, will be performed using group-sequential methods and Pocock alpha spending function, the hypotheses will be tested at a two-sided alpha of 0.031. A two-sided alpha of 0.028 will be used to test the hypothesis at the final analysis.
 
Data Evaluation
 
Analysis Population
 
The Intent-to-Treat (ITT) population, defined as all randomized subjects, will be the primary population for the analysis of primary and secondary efficacy endpoints.
 
The Per Protocol (PP) population, defined as all subjects who were not associated with a major protocol violation, will be used in supportive analyses of the primary and secondary endpoints.
 
In all efficacy analyses, covariate analyses will be conducted to assess the impact of various prognostic factors on closure and also to demonstrate the robustness of the primary analysis. Prognostic factors (i.e., covariates) will be included if they are found to be contributing factors (i.e., the individual covariate p-value is less than 0.05). Potential prognostic factors to be considered include:
 
 
• Ulcer area
 
• Age of Ulcer at Baseline
 
• Gender
 
• HbA1c
 
• Ulcer location
 
• Diabetes type
 
• Race
 
• Nicotine Use
 
• Baseline BMI
 

	
Primary Efficacy Analysis
 
The primary analysis will test the difference between the proportion of subjects who achieve complete wound closure by 13 weeks in the Active Treatment and SOC using the Cochran–Mantel–Haenszel (CMH) test.
 
For the primary efficacy analysis, missing values will be imputed using last observation carried forward (LOCF).

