11.2. Secondary Endpoint Analysis

To maintain the trial-wise Type I error rate at 0.05, a closed test procedure will be used for the secondary endpoints. For efficacy analyses, the first date of assessment of 100% re-epithelialization of the wound surface without detectable exudate or visible non-epidermal tissue will be used.

The order of the endpoints to be assessed will be as follows:

- Proportion of subjects with confirmed complete wound closure of the study ulcer during the 12-week Treatment Phase as assessed by computerized planimetry, during the Treatment Phase

A point estimate will be presented along with the exact 95% confidence interval based on the binomial distribution.

- Time to complete wound closure, as assessed by the Investigator.

The endpoint will be summarized by descriptive statistics. In addition, duration of time to complete wound closure/healed will be analyzed as a time-to-event endpoint. The survival curves will be estimated using the Kaplan-Meier method and compared using the log-rank test.

The derivations of time to complete wound closure/healed will be listed for each patient.

- Time to complete wound closure, as assessed by computerized planimetry.

The endpoint will be summarized by descriptive statistics. In addition, duration of time to complete wound closure/healed will also be analyzed as a time-to-event endpoint. The survival curves will be estimated using Kaplan-Meier method and compared using the log-rank test.

The derivations of time to complete wound closure will be listed for each patient.

- Rate of complete wound closure as assessed by computerized planimetry

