11.4. Prognostic Factors Assessments

For the ITT population, a covariate analysis will be conducted to assess the impact of various prognostic factors on ulcer closure and to demonstrate the robustness of the primary efficacy analysis. Prognostic factors (i.e., covariates) will be included if they are found to be contributing factors (i.e., the individual covariate p-value is less than 0.05). Potential prognostic factors to be considered include:

Baseline ulcer size	Diabetes type
Age of ulcer at baseline	Race
Gender	Nicotine Use
Recorded HbA1c	Baseline BMI
Ulcer volume	Ulcer location

Additional planned analyses include the use of Analysis of Covariance (ANCOVA) models which incorporate consideration of stratification factors (i.e., site and baseline ulcer area) to compare reduction in study ulcer size between the two treatment groups and Kaplan-Meier analysis to assess and describe the differences in the time to wound closure in the two treatment groups.

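### The confirmatory rate-of-closure ANCOVA has no fixed model: beyond the ulcer-size stratum, covariates are optional and depend on their own p-values

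*SAP*

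**What the plan says.** SAP 13.2.3 is the only place in the SAP that gives a test for the rate endpoint: "Analysis of Covariance (ANCOVA) will be used to compare the rate of wound closure". One term is unconditional: "The stratification factor, ulcer size at the time of randomization, will be used in this analysis". The remaining covariates, taken from section 11.4, "may also be incorporated in the model, if their presence is statistically significant", with the threshold at p ≤ 0.05.

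SAP 11.4 lists ten candidates, nine of them besides baseline ulcer size. Its own rule is similar but not optional: "Prognostic factors (i.e., covariates) will be included if they are found to be contributing factors", meaning that "the individual covariate p-value is less than 0.05". That analysis runs on the ITT population and is meant "to demonstrate the robustness of the primary efficacy analysis". Protocol 8.12.1 carries the same rule with nine candidates (ulcer volume is not among them). The protocol synopsis words it more widely: "In all efficacy analyses, covariate analyses will be conducted to assess the impact of various prognostic factors on closure".

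The status of the rate endpoint comes from SAP 11.2: "To maintain the trial-wise Type I error rate at 0.05, a closed test procedure will be used for the secondary endpoints". Rate of closure stands fourth of four in that order, as it does in protocol 8.12.1.

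**The concern.** A test that carries part of the trial-wise alpha needs one model, fixed before the outcome is seen. Here the model is open in two ways.

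- **Data-driven entry.** Whether a covariate qualifies depends on its association with the outcome in this trial.
- **Optional entry.** The word *may* leaves a qualifying covariate in or out at the analyst's choice. The SAP does not say whether screening is one at a time, joint or stepwise, or whether treatment is in the screening model. It does not say which result governs if the adjusted and stratum-only results differ.

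Nine optional covariates allow 2^9 = 512 models. The trial is open-label, and SAP section 8 states that personnel cannot be blinded, so masking does not limit the choice.

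At stake is the credibility of a claim on rate of closure and, less directly, the value of the section 11.4 analysis. A robustness check is weaker evidence when its covariates are picked from the same outcome data.

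**Working it through.** The documents give no figure for the covariate rule or for the power of the rate test, so there is none to reproduce on this point. The design they rest on does reproduce. A two-look calculation at 0.031 and 0.028 (two-sided, half the information at the first look, 102 per arm, 46% against 26%) gives overall alpha 0.0502, power 0.803 and early-stopping probability 0.479, the last as stated.

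**Inputs from the documents.** 207 subjects in the primary efficacy population (SAP 11.1.1); final level 0.028 (SAP section 6); entry threshold 0.05 (SAP 13.2.3); ten candidates, nine besides ulcer size (SAP 11.4). The SAP does not state the level for secondary tests, so using 0.028 is an assumption. Results at 0.05 are also given.

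**Step 1: chance that a noise factor enters.** If no candidate is prognostic and each is tested at 0.05, the probability that at least one enters is 1 − 0.95^9 = 37%. If continuous baseline size also counts as selectable, it is 1 − 0.95^10 = 40%.

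**Step 2: effect on the treatment test at 0.028.** Simulated ANCOVA with 207 subjects, residual SD 1, treatment effect 0 or 0.4, and factor coefficients 0.35, 0.25, 0.15, 0.15 and six zeros. The stratum is always in the model. The coefficients and effect size are assumptions.

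| | Stratum only | Selected at p ≤ 0.05 | Fixed set | Either model significant |
|---|---|---|---|---|
| False-positive rate | 3.0% | 3.2% | 2.8% | 4.0% |
| Power | 67% | 71% | 73% | not tabulated |

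The simulation error is about 0.2 points on the false-positive rates (for example √(0.03 × 0.97/6,000) = 0.0022 with 6,000 runs), so the first three entries of that row are not distinguishable from one another. Repeat runs gave 2.6–2.8% for stratum only, 2.9–3.1% for selected and 3.6–4.0% for either model. Power was 67–68% for stratum only and 71–73% for selected or fixed. With a true effect, the stratum-only and selected models gave different significance verdicts in about 9% of trials.

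**Step 3: sensitivity to prognostic strength, at nominal 0.05.** 10,000 null trials per scenario, with the variance explained by covariates assumed to be 0, 10% or 30%.

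| Analysis | Type I error |
|---|---|
| Stratum only | 0.044–0.053 |
| All candidates fixed in advance | 0.045–0.053 |
| Selection always applied | 0.047–0.054 |
| Smaller p-value of the two models, 0% explained | 0.051–0.053 |
| Same, 10% explained | 0.061–0.068 |
| Same, 30% explained | 0.074–0.081 |

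The two steps agree. If the 0.35 factor is taken as ulcer size, the other three prognostic factors in step 2 contribute 0.25² + 0.15² + 0.15² = 0.1075. Against residual variance 1, that is 0.1075/1.1075 = 9.7%, close to the 10% scenario. In the step 3 runs, the either-model rate at level 0.028 was 0.034–0.040 with 10% explained and 0.042–0.049 with 30%.

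**The case against.** The strongest reply is that the rule, if simply followed, does almost no harm. That stands: selection always applied keeps the error at 0.047–0.054, and even choosing the smaller p-value gives only 0.051–0.053 when no factor is prognostic. The inflation needs someone to fit both models and report the better one. The SAP does not plan this; it only fails to exclude it. The affected endpoint is also last in the order, so no later claim depends on it. These arguments limit the size of the problem. They do not supply a fixed model.

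Three stronger readings are tempting, and the documents do not support them.

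- **That the primary result is exposed.** The synopsis speaks of all efficacy analyses, but the CMH test in SAP 11.1 has no covariates selected by p-value, and the log-rank test in 13.2.3 is stratified by ulcer size alone. SAP 11.2 attaches none to the first secondary endpoint. Section 11.4 is supportive and cannot change the primary conclusion.
- **That the comparison is with an unadjusted model.** The ulcer-size stratum is always present. Leaving it out of the simulation gives about 65% power unadjusted against 74% selected, which overstates the contrast.
- **That a 37% or 40% chance of a noise factor entering measures the error inflation.** It does not, as step 3 shows.

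It is also fair to say that neither document ranks the candidates by prognostic strength. The power of the fixed set in step 2 therefore assumes that the right factors were chosen.

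**Conclusion.** The point holds for one confirmatory test, the last-ranked rate of closure. Its model is not fixed, because entry of up to nine covariates depends on outcome p-values and is optional even then. The excess false-positive risk is about one point at level 0.028 (roughly 3% to 4%) when covariates explain about 10% of the variance. It is negligible when they explain none and larger when they explain 30%. It arises from the freedom to choose between models; mechanical selection is not the cause. These sizes rest on assumed coefficients and on applying 0.028 to the secondary test. The lack of a fixed model does not depend on them. The change is worth making because it is nearly free, but it does not threaten the primary conclusion.

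**What to change.** In SAP 13.2.3, delete the rule that makes covariates optional and conditional on significance. Name one model for the confirmatory rate test: treatment, the ulcer-size stratum, and a short set of baseline covariates already collected. The sponsor should choose the set in advance and keep it whatever its significance; ulcer age, HbA1c and ulcer location are examples. The same edit should say whether site is a term, since the ANCOVA of ulcer-size reduction in 11.4 uses site and baseline area while 13.2.3 names only ulcer size.

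Use the same fixed set for the adjusted model that 11.4 offers as a robustness check of the primary result, and label any model selected by p-value exploratory. This also removes the mismatch between p ≤ 0.05 in 13.2.3 and p < 0.05 in 11.4.

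The cost is a few degrees of freedom among 207 subjects, plus aligning the matching text in the protocol synopsis and protocol 8.12.1. The sample size does not change.

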ENDPOINTS	
Primary Endpoint The primary endpoint of this study is the incidence of complete wound closure, as assessed by the investigator at or before Week 12 of the treatment phase.
 
Secondary Endpoints
 
 
1. Proportion of subjects with complete closure of the study ulcer at or before Week 12 as assessed by computerized planimetry.
 
2. Time to complete wound closure, as assessed by the investigator.
 
3. Time to complete wound closure, as assessed by computerized planimetry.
 
4. Rate of wound closure, as assessed by computerized planimetry.
 

	
Safety Endpoints Incidence of all adverse events (AEs) related to the study treatment, study ulcer or study procedures and all serious adverse events (SAEs).
 
Exploratory Endpoints Medical resource utilization associated with treatment of DFU and related complications, including:
 
 
• Interference of activities of daily living
 
• Interference of paid work (full-time or part-time)/school
 
• Physician office visits
 
• Emergency room visits
 
• Hospitalizations
 
• Home health nursing visits
 
• Skilled nursing facilities (SNF)
 
• Procedures
 
• Medication regimens to treat complications (analgesics, antibiotics, etc.)
 
• Diagnostic tests, imaging, etc.
 
• Treatment of AEs
 
• Use of durable medical equipment (off-loading/protective device, crutches, wheelchair, etc.)
 
• Dressing regimen and materials
 
• wound closure/healed status at the 4-week Follow-up visit
 

DATA COLLECTION
	
The following data will be collected:
 
 
• Medical Resource Utilization information
 
• Demographics
 
• Medical history
 
• Medications and non-study treatments
 
• AEs
 
• Physical examination
 
• Vascular perfusion tests, vital signs
 
• Ulcer assessments & treatments
 
• Supplies Usage
 
• Duration, size, exudate, location, infection, percent re-epithelialization (Documented or measured using clinical judgment, photography, and/or computerized planimetry)
 

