#### 5.15.4. Adverse Event Expectedness

If an AE is determined to be serious and related, either possibly, probably, or definitely related, to the study device or procedure, a determination of expectedness will be made. Expectedness is specifically related to the functioning of the product or the conduct of the procedure and is NOT related to whether the study team perceived that the AE might have happened in the subject. That is, the question is “Have we seen this SAE in relation to the product/procedure?” and is **not** “Did we think this SAE would happen in this subject?”.

A SAE is expected, that is “**Anticipated**” if the SAE is (1) related to the product or procedure **and** (2) the nature, severity, or frequency of the SAE has been seen previously either in personal experience or documented in literature. Note: The vast majority of related SAEs are Anticipated.

Conversely, a SAE is not expected, that is “**Unanticipated**” if the SAE is (1) related to the product or procedure **and** (2) the nature, severity, or frequency of the SAE has **NOT** been seen previously either in personal experience or documented in literature. Note: The vast minority of related SAEs are unanticipated.

Therefore, an unanticipated adverse device effect (UADE) is defined as any serious adverse effect on health or safety or any life-threatening problem or death caused by, or associated with, a device, if that effect, problem, or death was not previously identified in nature, severity, or degree of incidence in the investigational plan or IFU, or any other unanticipated serious problem associated with a device that relates to the rights, safety, or welfare of subjects.

[figure not shown]
The decision tree in figure 3 should be used when determining expectedness.

For the purposes of this study, the following AEs commonly occur in individuals with DM and DFUs and are thereby defined as Anticipated if they were to occur:

- Ulcer enlargement, tunneling and/or undermining
- Malodor
- Erythema
- Edema
- Maceration
- Excessive drainage
- Development of a new ulcer,
- Ulcer infection or abscess,
- Osteomyelitis
- Trauma/falls and
- Amputation

Questions about any AEs or SAEs should be directed to the sponsor for clarification; however, the ultimate decision for grading severity and expectedness resides with the study investigators.

Figure 3: SAE Expectedness Determination Decision Tree

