#### 8.2.4. Safety Endpoints

Safety will be assessed through reports of AEs and SAEs.

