### 8.12.4. Safety Analyses

The Safety population will be used for the analysis of safety endpoints.

Safety will be assessed through reports of AEs and SAEs. AEs related to the device, study ulcer and/or study procedures and all SAEs will be recorded.

All safety parameters will be summarized descriptively by treatment. No inferential statistics are planned.

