3.4. Safety Endpoints

Safety will be assessed through reports of AEs and SAEs, including incidence of all AEs related to the study treatment, study ulcer or study procedures and all serious adverse events.

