12.6. Safety Analysis

Safety will be assessed through reports of adverse events and serious adverse events. Adverse Events related to the device, study ulcer and/or study procedures and all Serious Adverse Events will be recorded.

All safety parameters will be summarized descriptively by treatment. No inferential statistics are planned.

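### SAP 13.2.3 adds a primary safety endpoint and Fisher tests that the rest of the plan does not support, and the tested events can be expected only in the PriMatrix arm

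*SAP*

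**What the plan says.** Three places define safety without ranking any safety endpoint as primary. Protocol 8.2.4 reads "Safety will be assessed through reports of AEs and SAEs". The protocol synopsis lists the incidence of related AEs and of all SAEs. SAP 3.4 follows them: "Safety will be assessed through reports of AEs and SAEs, including incidence of all AEs related to the study treatment, study ulcer or study procedures". The same sentence of SAP 3.4 also counts every serious event.

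On method, SAP 12.6 says "All safety parameters will be summarized descriptively by treatment. No inferential statistics are planned". Protocol 8.12.4 agrees: "No inferential statistics are planned".

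The Safety Data paragraph at the end of SAP 13.2.3 departs from all of this. It says "The primary safety endpoint for this study is any severe device-related complication where relationship to the device was assessed by the clinical event committee". Ratings of possible, probable or definite count. On the test it says: "Fisher's exact test will be used to compare incidence rates of serious device-related complications as well as for any device-related complication". The test is also to cover specific complications, which the paragraph does not list. The comparison is between the treatment group and the control group.

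On who judges events, Protocol 5.15.3 (Table 2) describes the top causality category through what the investigator feels. Severity and expectedness are settled separately in Protocol 5.15.4: "the ultimate decision for grading severity and expectedness resides with the study investigators". SAP 12.7 also leaves severity to the investigator.

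**The concern.** A programmer cannot follow both SAP 12.6 and SAP 13.2.3. If 13.2.3 is followed, the study report will carry a result labelled as the primary safety endpoint that the protocol never set. Its adjudicator is undefined, and the endpoint defined is not the first quantity tested.

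The test also has a design problem. Only one arm receives the study device, so a significant result can arise simply because only that arm's events can be attributed to PriMatrix. A reader could take it as evidence that the active arm is less safe. A non-significant result could equally be taken as reassurance. Neither inference follows from the comparison.

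**Working it through.** There is no planned figure to reproduce, because the paragraph gives no expected rate, sample size or power. The check is a comparison of the texts, followed by an illustration.

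**Text comparison**

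| Item | SAP 13.2.3, Safety Data | Elsewhere |
|---|---|---|
| Primary safety endpoint | Named | None in the protocol synopsis, Protocol 8.2.4 or SAP 3.4 |
| Judge of relatedness | Clinical event committee | Investigator's view (Protocol Table 2); no committee in the contents list, abbreviations, AE sections or statistics section |
| Severity or seriousness | Endpoint is severe, first test is on serious | Protocol 5.15.2 warns that severe does not imply serious |
| Inference | Fisher's exact test, open-ended list of complications | None planned (SAP 12.6, Protocol 8.12.4) |

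**Who can have a device-related event**

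1. The study device is PriMatrix (Protocol 5.17.2).
2. Controls receive saline gel, secondary dressings and an off-loading or protective device, without PriMatrix (Protocol 3.1 and 8.1).
3. The criteria in Protocol Table 2 time an event from application of the device.
4. The expected number of PriMatrix-related events in the control arm is therefore zero by design.

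**What Fisher's test does with a zero control count**

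Let a be the active-arm size, c the control-arm size and x the active-arm events, with 0 in controls. With the total x fixed, the probability that all events fall in the active arm is C(a, x) / C(a + c, x). The opposite extreme has probability C(c, x) / C(a + c, x). The two-sided p-value is the first term, plus the second if the second is no larger.

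The only sample size available for illustration is the 207 patients of the primary efficacy population (SAP 11.1.1). That is not the safety population, whose size is not stated. The near-equal splits below are assumptions.

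| Active / control | Events | Calculation | p |
|---|---|---|---|
| 104 / 103 | 5 vs 0 | 0.0305 + 0.0290 | 0.0595 |
| 104 / 103 | 6 vs 0 | 0.0149 + 0.0141 | 0.0290 |
| 103 / 104 | 4 vs 0 | 0.0595 (opposite extreme, 0.0619, is larger and not added) | 0.0595 |
| 103 / 104 | 5 vs 0 | 0.0290 (opposite extreme, 0.0305, is larger and not added) | 0.0290 |

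Moving one subject between arms changes the threshold from 6 events to 5. At 102, 120 or 128 per arm the threshold is 6 (p = 0.029).

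If the true active-arm rate is assumed to be 2%, 5% or 10%, the chance of p ≤ 0.05 is about 2%, 42% or 95% at 104/103. At 103/104 it is about 6%, 59% or 98%. With the control count at zero, these chances depend only on the active-arm rate and the arm sizes. No complication rate in the control arm enters.

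**The case against.** Several counter-arguments have force.

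- **The committee may exist.** It could work under a separate charter. The documents show only that it is undefined, so a reader who infers that the endpoint has no data source, or cannot be computed, goes too far. A charter would still leave the unsupported endpoint, the severe/serious switch, the conflict over inference and the one-sided comparison.
- **Controls do receive a device.** They get an off-loading or protective device, and the top category of Protocol Table 2 covers study treatment, ulcer and procedures as well. SAP 13.1 reports eight subjects at one site who did not get their original assignments, and the SAP does not say whether safety is grouped by assignment or by treatment received. A zero control count is therefore expected but not guaranteed. The point concerns PriMatrix, which controls do not receive.
- **Shared ulcer events are not lost.** A reader might infer that infections or other events common to both arms would be missed. SAP 12.7 contradicts this: it summarises treatment-emergent events by arm, with separate SAE summaries, and compares the groups on AE incidence.
- **Efficacy is untouched.** These tests lie outside the primary comparison and the closed procedure for secondary endpoints, so no efficacy alpha is affected.

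What stands is the internal contradiction, the unsupported endpoint, the undefined committee and the uninformative test.

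**Conclusion.** The point holds as an inconsistency in the SAP that should be corrected. The text findings rest on no assumption beyond the documents as supplied. That the Fisher comparison is uninformative rests on reading device as PriMatrix, which is how the protocol uses the term study device.

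The numerical illustration should be read as *5 or 6 events, depending on the split*. A reader might want to fix the threshold at 6, with 5 falling short. The documents do not support that, because they give neither the safety population size nor the arm sizes, and the 5-event result reverses when one subject changes arm. The conclusion does not depend on the illustration.

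**What to change.** Delete the Safety Data paragraph from SAP 13.2.3, so that SAP 3.4, 12.6 and 12.7 govern safety. In SAP 12.7, state that the between-group comparisons of AEs and SAEs are descriptive; the present wording leaves this open beside SAP 12.6. Report PriMatrix-related events descriptively for the active arm, using the investigator's attribution.

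If a clinical event committee does exist, define it in the SAP and report its adjudications descriptively, again without a between-arm test of device-related events.

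The cost is one deleted paragraph and about two added sentences. It removes no analysis that the protocol promised. The deletion does not settle a neighbouring question, namely whether all SAEs or only related ones are recorded: the protocol synopsis and Protocol 5.15.1 and 5.15.5 differ on this and must be reconciled separately.
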